This study is a sub-study of an “Ocular Surface and glaucoma. A randomized study of IOP reducing eye drops versus surgical intervention” study (REK no. 253485). Invited to participate in the study are men and women between 50 and 75 years of age with early POAG, diagnosed in agreement with the European guidelines for glaucoma diagnoses and staging of the disease, with MD loss of less than 5 dB on visual fields and with a clinically significant cataract eligible for surgery, who come for a routine glaucoma follow-up examination and a presurgical assessment for cataract extraction at the ophthalmology practice of Ifocus Øyeklinikk in Haugesund, Norway, in the period between August 2021 and February 2022.

Exclusion criteria:

- Recent changes (<3 months) in the treatment with topical IOP-lowering medications (i.e., active pharmacological substance, dosage, preservatives) based on the patient medical journals.
- Use of more than one IOP-lowering eyedrops with different active pharmacological substances based on the patient medical journals.
- Self-reported OSD comorbidity defined as an autoimmune or inflammatory disease, such as Sjogren’s syndrome or Rheumatoid Arthritis (RA), or any other systemic disease that can directly affect the ocular surface.
- Conditions that may confound the results of the study:
 - Self-reported acute or chronic diseases such as connective tissue disease, clinically significant atopic disease, diabetes type 1 and 2, immunocompromised, or any other such condition.
 - Manifest corneal disease, dystrophy, or scarring based on the clinical exam.
 - Corneal ectasia based on the clinical exam.
 - Lid deformities based on the clinical exam.

- Recent intra- or extra-ocular surgery based on the patient medical journals.
- Previous refractive procedures like LASIK, LASEK, or radial keratotomy based on the patient medical journals.
- A previous corneal transplant, DSAEK, lamellar keratoplasty, or similar procedure based on the patient medical journals.

Recruitment:

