Recruitment of subjects will take place in the ophthalmologic practice of Ifocus Øyeklinikk in Haugesund, Norway. This study is a sub-study of an “Ocular Surface and glaucoma. A randomized study of IOP reducing eye drops versus surgical intervention” study (REK no. 253485), and the participants in this study will be recruited from subjects that have given their consent to participate in the main study. Patients who come for follow-up glaucoma controls with visual field examination in our clinic and meet all criteria for inclusion will be invited to participate in the study. Eligible patients will be given oral and written information about the study together with a consent form (Appendix 1). The recruited patients’ names will be replaced with unique randomized three-digit ID numbers to ensure the anonymity of the participants. The key list that links patients’ names with ID numbers will be deleted five years after the completion of the study. The aim is to recruit 30 subjects (60 eyes), which is a feasible number of subjects to perform a full ocular surface assessment on in the chosen timeframe of six months.

Variables:

Outcome variables:

OSD-related disability (The Ocular Surface Disease Index (OSDI)) is defined as an impairment caused by OSD that makes it more difficult for an individual to perform daily activities. Operationally, it is defined as the self-reported frequency of ocular symptoms (3 items), visual function (6 items), and environmental triggers (3 items) measured by means of The Ocular Surface Disease Index (Schiffman, Christianson, Jacobsen, Hirsch, & Reis, 2000), which is a validated questionnaire that has been proven to accurately differentiate between normal, mild to moderate, and severe dry eye disease. It measures the frequency of symptoms with one week recall period. The OSDI is registered in whole numbers on a numerical scale from 0 (0=no disability) to 100 (100=complete disability).

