Bulbar redness or conjunctival hyperemia is defined as vasodilatation of the conjunctival blood vessels. Vasodilatation is associated with many ocular conditions, inflammation, and irritation. Operationally, bulbar redness or conjunctival hyperemia is defined as bulbar and limbal redness measured objectively with Oculus Keratograph 5M (OCULUS, Inc). R-Scan is an integrated software that detects the blood vessels in the conjunctiva and evaluates the degree of redness. Bulbar and limbal redness is measured in 0.1 steps on a numerical scale from 0 to 4.0, where 0 represents no bulbar redness and 4.0 represents severe bulbar redness according to the integrated JENVIS Pro Dry Eye Report (Oculus Keratograph 5M, OCULUS, Inc.) software grading scale for the right and the left eye.

Tear Meniscus Height is defined as the volume of tear fluid that is accumulated along the lid margins in an open eye. Operationally, it is defined as the height of the tear prism on the lower eyelid margin in line with the pupil center measured objectively from a single photograph taken with Oculus Keratograph 5M (OCULUS, Inc) that has an integrated ruler and various magnification options. It is measured in millimeters and registered with two decimals on a numerical scale for the right and the left eye.

Tear production (Schirmer 1 test) is defined as the rate of physiological production of tears secreted by all lacrimal glands in the eye. Operationally, tear production is defined as the amount of wetting that can be observed on a standardized strip of non-toxic filter paper (TearFlo™) applied to the temporal part of the lower eyelid of both eyes for 5 minutes. The Schirmer test is a diagnostic test that is performed without anesthesia. It supposedly measures both basal and reflex tear production. Wetting is measured in whole numbers of millimeters and registered on a numerical scale for the right and the left eye.

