Corneal sensitivity is defined as the ability of the cornea to sense a variety of stimuli. Operationally, it is defined as the threshold for corneal surface to sense the touch of a fine nylon filament (0,12 mm) applied to the corneal apex by means of a Cochet-Bonnet Aesthesiometer (Luneau Technology Group). The length of the nylon filament can be adjusted (from 60 mm (highest sensitivity) to 5 mm (lowest sensitivity)). It is measured in millimeters and registered with one decimal on a numerical scale for the right and the left eye.

Meibomian gland dropout is defined as partial or total loss of acinar tissue of the meibomian glands and its function in the upper and lower eyelid. Operationally, meibomian gland dropout is defined as changes in the morphological appearance in the meibomian glands of the upper and the lower eyelid evaluated by means of infrared trans-illumination of the lids using an Oculus Keratograph 5M (OCULUS, Inc). Gland tissues are made visible using Meibo-Scan software and classified on the Meiboscale grading scale from a photograph taken with Oculus Keratograph 5M (Pult & Riede-Pult, 2013). It is registered in whole numbers on an ordinal scale that ranges from 0 to 4 (0=0% loss; 1= \leq 25%; 2=26%-50%; 3=51%-75%; 4= \rightarrow 75%) for the right and the left eye.

Predictor variables:

Preservative is defined as a substance or a chemical that is added to pharmaceutical drugs and other products to prevent decomposition by microbial growth or by undesirable chemical changes. Operationally, a preservative is defined as any of the following substances in the specification of the prescribed eye drops during the period of three months before inclusion into the study: Benzalkonium chloride, Polyquaternium-1, and Boric acid. The preservative is registered on a dichotomous scale where preservative=1 and no preservative=0.

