Active pharmacological substance is an ingredient used in a finished pharmaceutical product, intended to provide pharmacological activity or to otherwise have a direct effect in the diagnosis, cure, treatment, or prevention of disease. Operationally, the active pharmacological substance is defined as any of the following substances in the specification of the prescribed eye drops during the period of 3 months before inclusion into the study: prostaglandin analogs, beta-blocker, carbohydrase inhibitor, or alfa-2-agonist. The active pharmacological substance used by the patients will be known from the patient history and will be noted on a nominal scale (1= prostaglandin analogs, 2=beta-blocker, 3=carbohydrase inhibitor, 4= alfa-2-agonist).

The duration of the treatment is defined as the period in which the patient has been treated with the same pharmacological substance. Operationally, it is defined as information about the duration of the treatment collected from the medical records and registered on a numerical scale with the whole number of months of use.

Self-reported compliance is defined as an act complying or adhering to requirements (prescribed treatment). Operationally, it is defined as self-reported adherence to taking drops in agreement with the prescription measured by means of a simple interview question of how often one may skip a dose (0: Less than once or twice a month; 1: Once or twice a month; 2: Approximately once a week; 3: More than once a week). It will be registered on an ordinal scale.

Other variables:

Age will be registered as the whole number of years on a numerical scale.

Sex will be registered as female=1 and male=0 on a dichotomous scale.

Methods:

Recruitment:

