Subjects included in this study will undergo a comprehensive tear film evaluation on both eyes. All examinations will be performed by an experienced observer ([name]) in the fixed order from the least to the most invasive one. Firstly, **OSD-related disability (OSDI)** (Appendix 2), and **The nature of the symptoms (SPEED II)** (Appendix 3) will be examined by means of questionnaires. The patient will be given approximately 5 minutes to complete the questioners. The examiner will be in the room with the patient and will provide only a general explanation. The examiner will avoid interpreting or rephrasing the questions. The OSDI questioner has shown good specificity (0.83) and moderate sensitivity (0.60) when differentiating between dry eye disease patients and healthy patients (Schiffman et al., 2000). The sensitivity and specificity for the SPEED II questioner are 0.90 and 0.80 (Ngo et al., 2013). Thereafter, clinical examinations will be performed on the right eye followed by the left eye in this order: **Tear film osmolarity, Non-invasive Keratograph tear break-up time (NIK BUT), Bulbar redness, Tear Meniscus Height, Tear production (Schirmer 1 test), Ocular surface staining (OSS), Meibum quality, Meibum expressibility, Corneal sensitivity, Meibomian gland dropout.** **Tear film osmolarity** will be measured with The TearLab Osmolarity System by TearLab Corporation that has a precision (CV) of 1,5% with a standard deviation (Stdev) of 5.0 mOsm/L and accuracy of $r^2=0,95$. Tear collection will be performed at the lateral (temporal) extent of the eyelid, and the test card should touch the lower temporal tear meniscus. **Non-invasive Keratograph tear break-up time (NIK BUT), Bulbar redness, and Tear Meniscus Height (TMH)** will be measured with The Oculus Keratograph 5M by OCULUS, Inc. The patient will be instructed to place head correctly in the chinrest, and when the Keratograph is aligned with the patient's face, the patient will be instructed to blink twice. After the second blink, the measurement of the NIK BUT will automatically begin. The patient will be encouraged to keep their eyes open as long as possible without blinking. The

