
Analyses:

The results of the comprehensive tear film evaluation will be recorded in the patient journal system (Infodoc Plenario) used at the Ifocus Øyeklinikk, Haugesund, Norway. The data collected with the Oculus Keratograph 5M by OCULUS, Inc. will be stored in a separate database called Oculus Patient Data Management. Once measurements are performed, data related to the study will be transferred from the patient journal to a data registration form (Appendix 4). The names of the patients will be replaced with ID numbers. All data will be transferred to and organized in a database (Excel, Microsoft Inc.). To identify empty cells or unrealistic values, an algorithm in Excel will flag the cells in question. A quality-assured version of the database will constitute the basis for statistical analyses. For variables measured on a numerical scale, these summaries will include the sample size, as well as the mean, standard deviation, median, minimum, and maximum. For variables measured on a categorical scale, summaries will provide the number and percentage of subjects who provided each score. Preliminary considerations of the data will include the investigation as to whether any transformation (i.e., logarithmic) should be applied prior to the statistical analyses. For categorical data, the sparseness of the data across categories will be considered, and the combination of categories prior to statistical analysis will be applied where deemed appropriate. For variables measured on a continuous scale, the statistical significance of the difference

between groups will be investigated using an Analysis of Variance (ANOVA) with appropriate post-hoc testing. For variables measured on an ordinal categorical scale, the Kruskal-Wallis signed-rank test will be employed. Questionnaire data will be analyzed using current standards. The statistical analyses will be performed using SPSS version 24. All statistical tests of hypotheses will employ a level of significance of $\alpha=0.05$. Odds ratios with 95% confidence intervals may also be used.

Project management and organization:

Principal investigator: [name]

Project manager: [name]

Resources, equipment, and physical facilities:

All equipment is available in the ophthalmic practice Ifocus Øyeklinikk in Haugesund, Norway, where the study will take place:

- The TearLab Osmolality System by TearLab Corporations.
- The Oculus Keratograph 5M by OCULUS, Inc.

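### The unit of analysis for the ocular surface signs is not fixed: 60 eyes are counted and only independent-observation methods are named, so an eye-level analysis would be anti-conservative

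*Protocol*

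**What the plan says.** The Recruitment section under the study sample sets the target: "The aim is to recruit 30 subjects (60 eyes), which is a feasible number of subjects". It gives two counts, and the only justification is feasibility.

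The Measurements section confirms that both eyes are examined: "Subjects included in this study will undergo a comprehensive tear film evaluation on both eyes". Under Outcome variables, the four signs that define ocular surface disease in the hypotheses are each registered by eye. The Schirmer 1 entry, for example, reads: "Wetting is measured in whole numbers of millimeters and registered on a numerical scale for the right and the left eye". The symptom questionnaires differ in that each gives one score per patient: "The OSDI is registered in whole numbers on a numerical scale from 0", and likewise for SPEED II.

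Under Predictor variables, exposure is a single value with no right/left entry. For preservative: "The preservative is registered on a dichotomous scale where preservative=1 and no preservative=0". The active substance "will be known from the patient history and will be noted on a nominal scale". Duration is a number of months from the records, and compliance is the answer to one interview question. The exclusion criteria also remove patients with "Use of more than one IOP-lowering eyedrops with different active pharmacological substances based on the patient medical journals".

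The Analyses section says that, for continuous variables, the difference "between groups will be investigated using an Analysis of Variance (ANOVA) with appropriate post-hoc testing". It names Kruskal-Wallis for ordinal variables and allows odds ratios with 95% intervals. It gives no rule for two eyes of one patient. The hypotheses compare frequencies in patients, and the categorical summaries count subjects.

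**The concern.** Two eyes of one patient tend to be alike. When the predictor takes the same value for both eyes, the second eye adds little information about its effect. ANOVA, Kruskal-Wallis and a standard odds ratio would nevertheless treat the second eye as a new independent observation. Standard errors then come out too small, and false-positive findings become more frequent than the stated 5%.

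The protocol leaves this route open. It prints the eye count beside the sample target, stores the signs by eye and names methods with no step for pairing.

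The gap matters even if patients are meant. A subject with staining in one eye only has no defined place in a table of subjects, so the answer to research question 1 (occurrence of signs) depends on a rule that is not stated.

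**Working it through.** **The plan's own figure.** 30 subjects x 2 eyes = 60 eyes. No effect size, standard deviation, event rate or power is given, so there is no sample size calculation to reproduce.

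**Inputs.** From the protocol: 30 patients, m = 2 eyes each, predictors constant within patient, alpha = 0.05 (taken as two-sided, since sidedness is not stated). Assumed: a between-eye correlation r of 0.5 to 0.9 and, for the simulation, groups of 15 and 15 patients.

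**Formulas.**
- Design effect: DE = 1 + (m - 1)r = 1 + r.
- Effective sample: 60/DE.
- Actual two-sided error at nominal 5%: 2 x (1 - Phi(1.96/sqrt(DE))).
- Fraction by which a nominal 95% interval is too narrow: 1 - 1/sqrt(DE).

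| r | DE | Effective n | Actual error | Actual coverage | Interval too narrow by |
|---|---|---|---|---|---|
| 0 | 1.0 | 60 | 5.0% | 95.0% | 0% |
| 0.5 | 1.5 | 60/1.5 = 40.0 | 11.0% | 89.1% | 1 - 1/1.225 = 18% |
| 0.7 | 1.7 | 60/1.7 = 35.3 | 13.3% | 86.7% | 1 - 1/1.304 = 23% |
| 0.9 | 1.9 | 60/1.9 = 31.6 | 15.5% | 84.5% | 1 - 1/1.378 = 27% |

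**Simulation check** (no true effect, 15 v 15 patients, two eyes each). With eyes treated as independent, ANOVA rejected in 11.4%, 13.9% and 16.1% of 20,000 runs at r = 0.5, 0.7 and 0.9. Kruskal-Wallis rejected in 11.9%, 14.3% and 14.9% of 4,000 runs. A 20 v 10 split gave much the same for ANOVA: 10.6%, 13.4% and 16.2%. ANOVA on one mean per patient stayed between 4.6% and 5.2% across all these settings.

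**More than two groups.** For the four substance classes, with an assumed split of 15/8/4/3 patients, eye-level ANOVA rejected in 16.1%, 21.9% and 27.3% of runs. Primary hypothesis 3 could therefore be hit harder than the two-group figures show.

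**Sensitivity of research question 1 to the two-eye rule.** Let a proportion p of eyes be positive with between-eye correlation 0.5 (assumed). Then P(both eyes) = p^2 + 0.5p(1 - p), and P(either eye) = 2p - P(both eyes).
- p = 0.50: both = 0.25 + 0.125 = 37.5%; either = 100 - 37.5 = 62.5%.
- p = 0.22: both = 0.0484 + 0.0858 = 13%; either = 44 - 13 = 31%.
- p = 0.78: both = 0.6084 + 0.0858 = 69%; either = 156 - 69 = 87%.

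The values 22% and 78% are the ends of the prevalence range in the Introduction, used here as per-eye rates for illustration.

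**The case against.** The strongest reply is that the protocol never says eyes will be analysed as 60 independent units. A reader might infer that commitment from the eye count, but the text does not support it. The hypotheses compare patients, the summaries count subjects, no calculation uses 60, and the eye count can be read as examination workload. This stands, and it makes the error inflation conditional. It does not remove the gap, because the data are stored by eye, the tests are named, and nothing says how the two meet.

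A second reply is that a two-eye rule may be left to a statistical analysis plan. That is fair for detail. But this protocol itself states the eye count and names the tests, so its own text leaves the ambiguity.

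Three wider readings should be resisted:
- A reader might infer that all p-values are affected. OSDI and SPEED II are one score per patient, so primary hypotheses 2, 4 and 6 and secondary hypotheses 2 and 4 are untouched.
- A reader might infer that every clinical sign is registered by eye. Meibum expressibility has no right/left entry.
- A reader might infer that untreated fellow eyes would be counted as exposed. The protocol does not mention one-sided treatment. That would also be a separate problem (misclassification, which tends to dilute effects), and it conflicts with exposure being fixed within patient.

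Finally, the figures come from two-group comparisons of continuous outcomes. The hypotheses concern frequencies, duration is a numerical predictor, and secondary hypothesis 3 is adjusted. For those analyses the numbers indicate direction and rough size and are not exact.

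**Conclusion.** The concern holds in a conditional form. For the signs, the protocol counts eyes, records exposure by patient, names independent-observation methods and words its hypotheses in patients, without fixing the unit of analysis. If the named methods are run on the eye-level data as registered, type I error for primary hypotheses 1, 3 and 5 and secondary hypotheses 1 and 3 rises from 5% to about 11-16%. Intervals are about 18-27% too narrow, and the effective sample is about 40 to 32.

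This rests on an assumed between-eye correlation of 0.5 to 0.9 and two equal groups. At zero correlation there is no inflation, and with four unequal groups it is larger. If the analysis is by patient, the error rate is sound, but the per-patient definition of a positive sign still has to be fixed.

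**What to change.** In the Recruitment and Analyses sections, state that the sample is 30 patients and that the patient is the unit of analysis. For the signs, choose one of the following in advance:

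- **One value per patient.** For example, the mean of both eyes for continuous signs, and a pre-specified either-eye or worse-eye rule for graded or yes/no signs.
- **Both eyes in a model.** A GEE or mixed model clustered on patient. With only 30 clusters, a GEE should use a small-sample correction to its standard errors.

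The cost is about one paragraph, with no extra patients or measurements. There are two downsides. The apparent sample falls from 60 to 30. A worse-eye or either-eye rule gives a higher occurrence than a per-eye rate, so the chosen rule must be fixed beforehand and reported with the result.

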Signs and symptoms of OSD are often non-specific to the ocular surface and caused by allergic, pro-inflammatory, or toxic conditions (Stewart et al., 2011). Ocular surface toxicity, especially to benzalkonium chloride (BAK) preservative, has been established and thoroughly discussed in the literature, which is why preservative-free treatment options are increasingly advocated, especially in patients already presenting with OSD (Stewart et al., 2011; Zhang et al., 2019). Performing a comprehensive tear film assessment in glaucoma patients may be beneficial and lead to a better understanding of the disease. To the best of our knowledge, no studies performed a full ocular surface assessment in glaucoma patients on topical treatment with IOP-lowering eye drops.

Research objectives and significance:

The main objective of the study is to investigate signs and symptoms of ocular surface disease in patients on topical glaucoma medications.

The main objective of the study is based on the following research questions:

1. What is the occurrence of signs and symptoms of ocular surface disease (OSD) in patients with primary open-angle glaucoma (POAG) who have been on treatment with IOP-lowering eye drops for at least three months?
2. Is the occurrence of signs and symptoms of OSD in patients with POAG related to added preservatives in the IOP-lowering eye drops?
3. Is the occurrence of signs and symptoms of OSD in patients with POAG modified by the active pharmacological substance in the IOP-lowering eye drops?

4. Is the occurrence of signs and symptoms of OSD in patients with POAG related to the duration of the treatment with the IOP-lowering eye drops?

Based on research questions 2-4, the following hypotheses were formulated:

1. In a sample of patients with POAG, who have been on treatment with IOP lowering eye drops for at least three months, the frequency of signs of OSD, defined as hyperosmolarity, reduced NIKBUT, ocular surface staining, or reduced Schirmer 1 test, is greater in patients that are on eye drops with preservatives compared with those that are not.
2. In a sample of patients with POAG, who have been on treatment with IOP lowering eye drops for at least three months, the frequency of symptoms of OSD, defined as OSDI index ≥ 13 or SPEED II values >5 , is greater in patients that are on eye drops with preservatives compared with those that are not.

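### Every participant has an unoperated cataract, half the OSDI items concern visual function, and total OSDI ≥13 alone counts as OSD symptoms, so cataract-related difficulty can be recorded as ocular surface disease

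*Protocol*

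**What the plan says.** The Study population section of the protocol invites patients with early POAG and "with a clinically significant cataract eligible for surgery", who attend for glaucoma follow-up and "a presurgical assessment for cataract extraction". The questionnaires are therefore answered with the cataract still in place.

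Under Outcome variables, OSDI disability "is defined as an impairment caused by OSD that makes it more difficult for an individual to perform daily activities". It is measured as the "self-reported frequency of ocular symptoms (3 items), visual function (6 items), and environmental triggers (3 items". On registration the text says: "The OSDI is registered in whole numbers on a numerical scale from 0 (0=no disability) to 100 (100=complete disability".

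Under Research objectives and significance, the symptom endpoint is "the frequency of symptoms of OSD, defined as OSDI index ≥ 13 or SPEED II values >5". The same definition serves primary hypotheses 2, 4 and 6 and secondary hypotheses 2 and 4.

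Under Measurements, the protocol credits the OSDI with "good specificity (0.83) and moderate sensitivity (0.60) when differentiating between dry eye disease patients and healthy patients", and SPEED II with sensitivity 0.90 and specificity 0.80.

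Nothing in the protocol separates the two causes of visual difficulty. Cataract is not in the list of confounding conditions. Neither visual acuity nor cataract grade is among the outcome, predictor or other variables. The adjusted secondary hypotheses adjust only for preservative, substance and duration.

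**The concern.** The OSDI is defined as impairment that OSD causes, but it is given to people who all have a second, established reason for visual difficulty. A patient with a quiet ocular surface and a troublesome cataract can score on the six visual-function items, pass 13, and be recorded as having OSD symptoms.

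Two results are at stake. The first is research question 1, the occurrence of symptoms, which would be too high. The Study sample section names POAG patients on topical treatment as the target population without mentioning cataract, so readers could put the excess down to the drops. The second is the set of symptom comparisons by preservative, substance, duration and compliance. Positives that have nothing to do with those factors pull the groups together. The sign endpoints (osmolarity, NIKBUT, staining, Schirmer) are not touched by this mechanism.

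**Working it through.** The protocol gives no calculated figure to reproduce on this point; the 30 subjects are a feasibility number.

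**1. Share of visual items.** 6 / (3 + 6 + 3) = 6/12 = 50%.

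**2. Reaching the cut-off on visual items alone.** The protocol does not state item scoring. Assume 12 equally weighted items scored 0 to 4, so OSDI = 100 × sum / 48.
- Most that the visual items can contribute: 100 × 24/48 = 50 points. The cut-off is 13/50 = 26% of that.
- A score of 1 on each visual item and 0 elsewhere: 100 × 6/48 = 12.5. This is negative unrounded, and positive if halves are rounded up to whole numbers. No rounding rule is given.
- One point more: 100 × 7/48 = 14.6, positive under any rounding.

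**3. The OR rule.** A patient is positive if either questionnaire is positive, so SPEED II cannot remove an OSDI false positive. Equally, cataract changes the classification only of patients who are negative on SPEED II.

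**4. Illustration for the composite.** Cited inputs: OSDI sensitivity 0.60 and specificity 0.83; SPEED II 0.90 and 0.80; OSD prevalence 22% to 78% (Introduction). Assumptions: the cited accuracies apply at the planned cut-offs; the two questionnaires err independently given OSD status; cataract lowers OSDI specificity to 0.70 or 0.50 and leaves sensitivity unchanged.
- Composite sensitivity: 1 − (1 − 0.60)(1 − 0.90) = 0.96.
- Composite specificity: OSDI specificity × 0.80.
- Apparent occurrence: p × 0.96 + (1 − p)(1 − composite specificity).
- Observed group difference: true difference × (0.96 + composite specificity − 1), if misclassification is the same in both groups.

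| OSDI specificity | Composite specificity | Apparent, true 22% | Apparent, true 50% | Apparent, true 78% | True 30-point difference becomes |
|---|---|---|---|---|---|
| 0.83 (cited) | 0.664 | 47.3% | 64.8% | 82.3% | 18.7 points |
| 0.70 (assumed) | 0.56 | 55.4% | 70.0% | 84.6% | 15.6 points |
| 0.50 (assumed) | 0.40 | 67.9% | 78.0% | 88.1% | 10.8 points |

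At a true 22%, the shift from 0.83 to 0.70 is 0.78 × (0.664 − 0.56) = 8.1 points, or 2.4 of 30 subjects. The shift to 0.50 is 0.78 × (0.664 − 0.40) = 20.6 points, or 6.2 of 30. At a true 78% the shifts are 0.22 × 0.104 = 2.3 points and 0.22 × 0.264 = 5.8 points.

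**5. Whether SPEED II can serve as the cleaner comparison.** Outcome variables lists four symptom types, frequency 0 to 3 and severity 0 to 4, which gives at most 4 × (3 + 4) = 28. The same paragraph states a scale of 0 to 64. The listed symptoms include no visual-function item, but the text does not show what fills the rest of the scale or which score the cut-off of 5 refers to.

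**The case against.** Several points on the other side stand.

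- **Visual items are not merely contamination.** The Introduction lists variable visual acuity and photophobia among the most common OSD symptoms. Dropping the visual items would discard some genuine OSD, and the documents give no validated cut-off for a six-item score. A reader might infer that the total OSDI should be removed from the endpoint. The documents do not support that.
- **The size is unknown.** Nothing says how often a cataract patient with a healthy ocular surface scores 13 or more. The 12.5 example is one boundary score under assumed scoring, not a measure of bias.
- **Calculating on the OSDI alone exaggerates the dilution.** With sensitivity 0.60, a true 30-point difference would become 30 × (0.60 + specificity − 1) = 12.9, 9.0 or 3.0 points. A reader might conclude that the comparisons are nearly wiped out. But the endpoint is the composite, where the figures are 18.7, 15.6 and 10.8.
- **SPEED II has its own defect**, the 28 against 64 discrepancy, so it is not a ready replacement.
- **Subscale reporting can be left to an SAP**, and the Analyses section defers questionnaire handling to prevailing standards. So the absence of subscale reporting is no defect in itself. It does not answer the point, because the hypotheses already fix the total-score cut-off as sufficient.

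The reply that the OSDI is validated carries less weight: the accuracy the protocol cites is against healthy patients, not patients with cataract.

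**Conclusion.** The concern holds in direction. The premises are in the protocol: all participants have an unoperated surgical cataract, half the OSDI items concern visual function, and OSDI ≥13 is sufficient on its own. Symptom occurrence is probably overstated, and the symptom comparisons may be diluted.

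The size cannot be derived. The table shows an excess of about 2 to 21 percentage points over true occurrence of 22% to 78%, and it rests on assumed OSDI specificities, independence of the questionnaires and unchanged sensitivity. If cataract also pushes patients with true OSD over the cut-off, occurrence rises further and the dilution is smaller.

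A reader might also infer that cataract severity, rising with age, creates a false link with treatment duration (primary hypothesis 6). That is only a possibility: the documents show neither that severity tracks age among patients aged 50 to 75 who all already qualify for surgery, nor that duration tracks age. Age is recorded, so the question can be examined.

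**What to change.** Keep the stated composite and add the following.

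1. Report the symptom result based on SPEED II >5 alone beside the composite. First reconcile the 0 to 64 scale with the listed items (maximum 28) and state which score the cut-off of 5 applies to.
2. Report the OSDI ocular-symptom and environmental-trigger items (3 + 3) as a score, separately from the six visual-function items. Treat it as a supporting result without a cut-off.
3. Apply ≥13 to the unrounded OSDI.
4. State that total OSDI is not specific to OSD in a sample where everyone has a cataract. Without that statement, do not attribute patients positive on OSDI only to OSD or to the eye drops.

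The cost is scoring, a little more analysis and some wording; the items are already collected, so no added visit, subject or test is needed. The drawback is that the non-visual score has no validated cut-off in the documents and may miss genuine visual symptoms of OSD, which is why it supports the composite and does not replace it.
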